1.5.5. Nonevaluable

In a subject who does not have evidence of PD, the occurrence of any of the following conditions indicates a response status of NE:

• There are no images or inadequate or missing images, defined as the inability to visualize > 25% of index disease and > 50% of non-index disease.

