14.2. Statistical and Analytical Plans

Detailed methodology for summary and statistical analyses of the data collected in this trial will be documented in a statistical analysis plan (SAP). The SAP may modify the plans outlined in the protocol; any major modifications of the primary endpoint definition and/or its analysis will be described in the SAP and the final clinical study report. Additional statistical analyses other

Version 9, 18 Feb 2020

than those described in this section may be performed if deemed appropriate and will be described in the SAP. Where individual data points are missing because of insufficient samples, dropouts, or other reasons, the data will be analyzed based on reduced denominators.

Results will be summarized by dose cohorts.

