14.11. Missing Data and Imputation

Missing data generally will not be imputed except those defined in the SAP.

Protocol: LAM-002A-NHL-CLN01

Version 9, 18 Feb 2020

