1.4. Identification and Follow-up of Tumor Lesions and Organomegaly

1.4.1. Index Lesions

Up to 6 lesions (e.g., lymph nodes, liver or spleen nodules, and/or other circumscribed extranodal masses) should be selected as index lesions that will be used to quantitate the status of the disease during study treatment. Ideally, the index lesions should be located in disparate regions of the body and include mediastinal, abdominal, and retroperitoneal areas of disease whenever these sites are involved. For subjects with FDG-avid lymphomas undergoing PET, selection of FDG-avid lesions is preferred.

Index lesions will be measured and recorded at baseline and at the stipulated intervals during treatment. The largest cross-sectional dimensions (i.e., the LD × LPD will be recorded (in cm) for each index lesion. Using the LD and LPD, the product of the perpendicular diameters (PPD) for each index lesion will be calculated. The PPDs and the SPDs for all index lesions will be calculated and recorded. The baseline and nadir PPDs of individual lesions and the baseline and nadir SPDs will be used as references by which objective tumor response and progression will be characterized during treatment. All PPD and SPD measurements will be reported in centimeters squared.

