1.4.3. Extranodal Index Lesions

An extranodal mass may be selected as an index lesion if it is both abnormal and measurable at baseline. An extranodal mass of any size is considered abnormal. It is considered measurable at baseline if it has 2 perpendicular diameters that can be accurately measured in cross section with the LD being ≥ 1.0 cm and the LPD also being ≥ 1.0 cm.

At follow-up timepoints, the PPD of each single extranodal index lesion and the SPD of all extranodal index lesions will be considered. Because extranodal index lesions that have one or both diameters < 0.5 cm and > 0 cm cannot be reliably measured, a default value of 0.5 cm will be assigned for each diameter that meets these criteria and the resulting PPD will be used in SPD calculations. If an extranodal lesion is no longer clearly visible, it will be considered resolved and its PPD will be defined as 0 cm².

If an extranodal lesion that had resolved (i.e., had a PPD of 0 cm²) subsequently reappears, the subject will be considered to have PD. A new extranodal lesion of any size that appears at a site that was not previously involved with lymphoma and is discernible to the radiologist by CT scan will be considered PD.

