1.5.2. Partial Response

To satisfy criteria for PR, all of the following conditions must be attained:

- No evidence of new disease
- A \geq 50% decrease from baseline in the SPD of the index nodal and extranodal lesions
- No increase from the nadir in the size of non-index disease
- No increase from the nadir in the size of the liver or spleen and no new liver or spleen enlargement
- If PET performed:
 - Typically FDG-avid lymphoma: if no baseline PET scan or if the PET scan was positive before therapy, the on-treatment PET is positive in ≥ 1 previously involved site– i.e., score of 4 (uptake moderately > liver) or score of 5 (uptake markedly > liver) on the Deauville 5-point scale but with reduced uptake compared with baseline. If baseline PET was performed and was negative, there is no new PET evidence of disease.
 - Variably FDG-avid lymphoma/FDG-avidity unknown: if no pretreatment PET scan or if the pretreatment PET scan was negative for lymphoma, CT criteria should be used in assessing the tumor during treatment. If the PET scan was positive before therapy, the on-treatment PET is positive in ≥ 1 previously involved site.
- Persistence of bone marrow involvement in a subject who meets other criteria for CR based on the disappearance of all nodal and extranodal masses

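### The NHL nonevaluable rule joins its two limits with *and*, so a scan with much of the index disease unseen can stay evaluable and be given a response category

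*Combined protocol and SAP*

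**What the plan says.** Appendix 2, section 1.5.5 gives the NE conditions for NHL: "There are no images or inadequate or missing images", where inadequate or missing is "defined as the inability to visualize > 25% of index disease and > 50% of non-index disease". The introduction to section 1.5 also describes NE in general terms, as the category for too little information, but sets no threshold.

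Section 1.4.1 says that up to six lesions "should be selected as index lesions that will be used to quantitate the status of the disease during study treatment", and "The PPDs and the SPDs for all index lesions will be calculated and recorded". Section 1.4.4 records non-index lesions only where they exist at baseline, so a subject may have none.

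The size part of PR (section 1.5.2) is a fall of at least 50%, stated as a "decrease from baseline in the SPD of the index nodal and extranodal lesions". The other PR conditions cover new disease, non-index disease, liver and spleen, and PET if done.

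The one written zero rule for a lesion that is not seen is in section 1.4.3: "If an extranodal lesion is no longer clearly visible, it will be considered resolved and its PPD will be defined as 0 cm²". Section 1.4.2 has no such rule for nodes.

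Best overall response is the best on-treatment assessment (section 1.5), made by the investigator (protocol section 5.5). No confirmatory scan is stated. Protocol section 14.3.1 counts a best overall response of NE as a failure in the full analysis set.

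**The concern.** An NE rule should stop a response being read from a scan that shows too little of the disease. With *and*, exceeding the index limit is not enough, because more than half of the non-index disease must be unseen as well. The index lesions decide the SPD, yet a scan can lose most of them and pass. For a subject without non-index disease the second limit cannot be exceeded, so the joint test never applies.

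The ORR is at stake. A subject who should count as a non-responder could be scored as a responder on one incomplete scan. The same artefact could set a falsely low nadir, and a later complete scan would then look like progression, which would affect duration of response and PFS.

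**Working it through.** **The plan's own figures.** The documents give no number for the NE rule itself. The nearest figures downstream are in section 14.1.2, and both reproduce.
- FL monotherapy boundary 8/20: the exact 1-sided 95% lower bound is 21.7%, in line with the stated 20% or more.
- 0/6 in a small cohort: the 1-sided 90% upper bound is 1 - 0.1^(1/6) = 31.9%, the stated 32%.

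**The NE rule.** Take six equal index lesions with k unseen, so the unseen index share is k/6. One unseen is 16.7%, two are 33.3%, three are 50%.
- With *and*, and 50% or less of non-index disease unseen (or none present): no value of k from 0 to 6 exceeds both limits, unless there are no images at all.
- With *and*, and more than 50% of non-index disease unseen: NE from k = 2.
- With *or*: NE from k = 2 whatever the non-index status.

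**Apparent SPD change.** This step assumes that unseen lesions count as 0 at follow-up and stay in the baseline SPD. If the seen lesions are unchanged, the change is -k/6. The shrinkage s that the seen lesions need to reach -50% is 1 - 0.5/(1 - k/6).

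| k unseen of 6 | Change if seen lesions are stable | Shrinkage of seen lesions needed for the PR size criterion |
|---|---|---|
| 0 | 0% | 50% |
| 1 | -16.7% | 40% |
| 2 | -33.3% | 25% |
| 3 | -50.0% | 0% |
| 4 | -66.7% | 0% |
| 5 | -83.3% | 0% |

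If the seen lesions are instead compared with their own baseline, stable disease gives 0% for any k below 6. The artefact therefore depends on the handling of unseen lesions as well as on the NE rule.

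**Nadir.** If a false -50% became the nadir, a return to the true SPD would be 1/0.5 - 1 = +100%, above the 50% increase that section 1.5.4 calls progression.

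**Effect of one false PR on a subject who otherwise counts as a non-responder.**
- 6-subject cohort: 1/6 = 16.7 points. The result 0/6 becomes 1/6, whose 1-sided 90% upper bound is about 51%: at p = 0.51, (1 - p)^6 + 6p(1 - p)^5 is about 0.10. An ORR of 35% is then no longer excluded.
- 20-subject FL cohort: 1/20 = 5 points. The result 7/20 (lower bound 17.7%, boundary not met) becomes 8/20 (21.7%, met).

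**Assumed frequencies.** The documents give none. Suppose a share f of true non-responders is scored as PR and the true ORR is 20%. The apparent ORR is 0.20 + 0.80f, and at a single look at N = 20 the chance of 8 or more responses is:
- f = 0: 0.032
- f = 2.5% (apparent ORR 22%): 0.054
- f = 5% (24%): 0.083
- f = 10% (28%): 0.171

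**The case against.** The strongest reply is that the documents do not actually produce the false PR.

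- **The general NE wording in section 1.5, and the requirement for sufficient assessments in sections 6.1.5 and 14.3.1, would catch such scans.** This stands in part. A careful assessor could use them. None sets a lesion threshold or overrides the specific definition in 1.5.5, and 14.3.1 itself refers back to NE.
- **SPD is defined over all index lesions, so with some unmeasured it cannot be computed.** This is a fair reading, but no text sends that outcome to NE. The zero rule in 1.4.3 concerns lesions no longer clearly visible. It does not require that the site was imaged, so it could be read to cover an unimaged extranodal lesion. For nodes nothing enters a zero.
- **The drafters may have meant either limit to suffice.** That is possible, and the text should then say so.

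A reader might go further and infer that omitting the abdomen and pelvis, with half the index lesions there, yields a PR. The documents do not support this. Section 1.5.2 requires no increase in liver or spleen and no new enlargement of either, and section 1.4.5 requires both organs to be reported at follow-up. Those conditions could not be affirmed from such a scan.

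A reader might also infer that the missing-data clauses create the -50%. Section 14.2 says "the data will be analyzed based on reduced denominators", and section 14.11 says "Missing data generally will not be imputed except those defined in the SAP". Neither clause is about lesions within an SPD. Entering zero would itself be an imputation, and a reduced denominator applied to lesions would give 0% change on stable disease.

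**Conclusion.** The defect in 1.5.5 is real on its literal wording. The joint limit lets a scan with much or all of the index disease unseen stay evaluable when 50% or less of non-index disease is unseen, and it can never be met by a subject with no non-index disease. This leaves room for a scan that should be NE to receive a response category.

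A false PR is a possible consequence, not an automatic one. It needs unseen lesions to be set to zero, or dropped only at follow-up, and all other PR conditions to hold. The -50% at three of six lesions also assumes equal lesions and no change in those seen; with unequal lesions, or some shrinkage, fewer missing lesions suffice.

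The effect per event is 16.7 points of ORR in a cohort of 6 and 5 points in one of 20. An upward bias in ORR is not demonstrated, because the frequency of such scans is unknown and the part of the document not available here may add a rule. The point concerns a secondary endpoint and the NHL criteria only; the CLL/SLL rule in section 2.5.5 has no joint threshold. It should be corrected because the rule feeds the ORR boundaries and the edit is small.

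**What to change.** In Appendix 2, section 1.5.5, replace *and* with *or*, and state that the non-index limit applies only if non-index disease was present at baseline.

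Add that an index lesion whose site was not imaged is missing, not 0 cm² and not resolved, so it may not contribute to an apparent SPD decrease or to the nadir.

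For a scan within the 25% tolerance, assign PR only if the fall of at least 50% still holds with the unseen lesion carried at its baseline or last measured value. This keeps the tolerance usable, which a ban on computing SPD change whenever any lesion is unmeasured would not. It is needed even with *or*: with 25% of baseline SPD unseen and counted as zero, a shrinkage of 1 - 0.5/0.75 = 33.3% in the seen lesions would reach the PR size criterion. With one of six equal lesions carried at baseline, the other five must shrink by 60%, since 1/6 + (5/6)(1 - 0.60) = 0.50.

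The cost is a few sentences and slightly more NE time points.

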2. CHRONIC LYMPHOCYTIC LEUKEMIA/SMALL LYMPHOCYTIC LYMPHOMA

2.1. Tumor Assessment Criteria

The determination of CLL/SLL response and progression will be based on standardized criteria (Hallek 2008), as recently updated (Cheson 2012).

2.2. Method of Assessment

In addition to clinical examination, imaging-based evaluation will be used in this study in all subjects enrolled. CT scan is the preferred method for radiographic tumor assessment. MRI scanning may be used at the investigator's discretion in subjects for whom this may be a preferred alternative to CT scanning; however, if MRI is performed, a non-contrast CT of the chest should be performed. Contrast-enhanced scanning is preferred, but iodine-containing or gadolinium contrast material may be omitted in subjects for whom use of a contrast agent would be medically contraindicated. Chest x-ray, ultrasound, endoscopy, laparoscopy, PET, radionuclide scans, or tumor markers will not be considered for response assessment.

Version 9, 18 Feb 2020

For radiographic evaluations, the same method of assessment and the same technique (e.g., scan type, scanner, subject position, dose of contrast, injection/scan interval) should be used to characterize each identified and reported lesion at baseline and during study treatment and follow-up. However, if a subject is imaged without contrast at baseline, subsequent assessments should be performed with contrast, unless the subject cannot tolerate the contrast.

All relevant clinical and radiographic information required to make each tumor status assessment must be made available for source verification as requested by the study sponsor.

2.3. Timing of Assessments

During screening, clinical, laboratory, and imaging-based tumor assessments should be performed within the specified screening period. Clinical tumor assessments should be performed at each designated clinical visit. On-study CT/MRI tumor assessments should be performed as indicated in Section 8.7. An end-of-study CT/MRI tumor assessment should be performed unless the subject already has radiographic confirmation of disease progression ≤ 4 weeks prior. If a subject permanently discontinues study drug prior to objective documentation of CLL/SLL progression, investigators should optimally attempt to obtain further follow-up at ~12-week intervals until CLL/SLL progression is documented or until the initiation of a new post-study therapy for the subject's CLL/SLL.

2.4. Identification and Measurement of Tumor Lesions and Organomegaly

2.4.1. Index Lesions

At baseline, up to 6 lymph nodes should be selected as index lesions that will be used to quantitate the status of the disease during study treatment. Ideally, the index lesions should be located in disparate regions of the body. Only peripheral nodes need be selected as index lesions. However, it is optimal if mediastinal and retroperitoneal areas of disease are assessed whenever these sites are involved.

Index lesions will be measured and recorded at baseline and at the stipulated intervals. The cross-sectional dimensions (the largest cross-sectional diameter, i.e., the LD \times LPD) will be recorded (in cm) for each index lesion. The product of the perpendicular diameters (PPD) (in cm²) for each index lesion and SPD (in cm²) for all index lesions will be calculated and recorded. The baseline SPD will be used as references by which objective tumor response will be characterized during treatment. The nadir LD of individual lesions and the nadir SPD will be used as references by which CLL/SLL progression will be characterized. All LD and LPD diameters will be reported in centimeters and all PPDs and SPDs will be reported in centimeters squared.

A nodal mass may be selected as a nodal index lesion if it is both abnormal and measurable at baseline. A lymph node lesion is considered abnormal if it has a single diameter that is > 1.5 cm and is considered measurable if it has 2 perpendicular diameters that can be accurately measured in cross section with the LD being ≥ 1.0 cm and the LPD also being ≥ 1.0 cm.

Index lesions measuring > 1.5 cm in the LD, regardless of the measurement of the LPD, will be prioritized during baseline index lesion selection.

Version 9, 18 Feb 2020

At follow-up timepoints, the LDs for individual lesions and the SPD of all nodal index lesions will be considered. Because nodal index lesions that have one or both diameters > 0 cm and < 1.0 cm cannot be reliably measured, a default value of 1.0 cm will be assigned for each diameter that meets these criteria and the resulting PPD will be used in SPD calculations. Based on this convention, a CR may be achieved even if an SPD value is > 0 cm², (i.e., if all lymph nodes measure < 1.0 cm²).

A new node that measures > 1.5 cm in any diameter or a new node that measures > 1.0 cm to ≤ 1.5 cm in the LD and measures > 1.0 cm in the LPD will be considered progressive disease.

In cases in which a large lymph node mass has split into multiple components, only those elements that are > 1.0 cm in ≥ 1 diameter will be considered abnormal and used in calculating the SPD. Progression of the lesion can only be based on the SPD of abnormal sub-components. Lesion sub-components that are considered normal but measurable will have the true PPDs calculated, with the result used only for calculating an accurate nadir. Similarly, lesion sub-components that are visible but neither abnormal nor measurable will have the default PPD of 1.0 cm^2 ($1.0 \text{ cm} \times 1.0 \text{ cm}$) stored only for the purposes of calculating the nadir SPD value.

If lesions merge, a boundary between the lesions will be established so the LD of each individual lesion can continue to be measured. If the lesions have merged in a way that they can no longer be separated by this boundary, the newly merged lesion will be measured bi-dimensionally.

2.4.2. Spleen and Liver

Both the spleen and liver will be assessed by CT/MRI scan and by physical examination at baseline and at the stipulated intervals during treatment. The baseline and nadir values for the longest vertical dimension (LVD) of each organ will be used as reference to further characterize the objective tumor response of the measurable dimensions of the CLL/SLL during treatment. All spleen and liver LVD measurements should be recorded in centimeters.

Physical examination of the spleen should comprise assessment of its LVD below the left costal margin by palpation. By physical examination, the spleen will be considered enlarged if it is palpable below the left costal margin. If the spleen is not palpable below the left costal margin, it should be assigned a value of 0 cm for physical examination assessment. By imaging, the spleen will be considered enlarged if it is > 12 cm in LVD (Bezerra 2005, Asghar 2011), with the LVD being obtained by multiplying the number of sections on which the spleen is visualized by the thickness of the sections (e.g., if the spleen is seen in 14 contiguous cross-sectional images with 0.5-cm thickness, the LVD is recorded as 7 cm).

For subjects with splenomegaly at baseline or at the splenic LVD nadir, respective response and progression evaluations of the spleen will consider only changes relative to the enlargement of the spleen (i.e., the portion of the LVD that is > 0 cm by physical examination or > 12 cm by imaging) at baseline or nadir, not changes relative to the total splenic LVD.

A 50% decrease from baseline (minimum decrease of 2 cm) in the enlargement of the spleen in its LVD or to \leq 12 cm by imaging, or regression to a spleen LVD of \leq 0 cm by physical examination, is required for declaration of a splenomegaly response. Conversely, an increase in splenic enlargement by \geq 50% (minimum increase of 2 cm) from nadir is required for declaration of splenic progression. Subjects with a normal spleen LVD (i.e., a LVD of \leq 0 cm by physical

Version 9, 18 Feb 2020

examination or ≤ 12 cm by imaging) at nadir will only be considered to have progressed if the spleen attains a LVD of > 14 cm by imaging or > 2 cm by physical exam.

Physical examination of the liver should comprise assessment of its LVD at the right midclavicular line by percussion. By physical examination, the liver will be considered enlarged if it is > 15 cm in LVD as assessed by percussion (Walker 1990). By imaging, the liver will be considered enlarged if it is > 18 cm in LVD (Erturk 2006).

A 50% decrease (minimum decrease of 2 cm) from baseline in the enlargement of the liver in its LVD or to \leq 18 cm by imaging, or regression to a liver LVD of \leq 15 cm by physical examination, is required for declaration of a hepatomegaly response. Conversely, an increase in liver enlargement by \geq 50% (minimum increase of 2 cm) from nadir is required for declaration of hepatic progression. Subjects with a normal liver LVD (i.e., a LVD of \leq 15 cm by physical examination or \leq 18 cm by imaging) at nadir will only be considered to have progressed if the liver attains a LVD of \geq 20 cm by imaging or \geq 17 cm by physical exam.

2.4.3. Non-Index Lesions

Any other measurable and abnormal nodal lesions not selected for quantitation as index lesions may be considered non-index lesions. In addition, non-measurable evidence of CLL/SLL such as nodal lesions with both diameters < 1.0 cm, extranodal lesions, bone lesions, leptomeningeal disease, ascites, pleural or pericardial effusions, lymphangitis of the skin or lung, abdominal masses that are not confirmed and followed by imaging techniques, cystic lesions, previously irradiated lesions, and lesions with artifacts may be considered as non-index disease.

The presence or absence of non-index disease should be recorded at baseline and at the stipulated intervals during treatment. If present at baseline, up to 6 non-index lesions should be recorded. The non-index disease at baseline will be used as a general reference to further characterize regression or progression of CLL/SLL during assessments of the objective tumor response during treatment. Measurements are not required and these lesions should be followed as "present" or "absent".

